## **Relationship between the Severity of Bronchiectasis and Exercise Capacity after a Pilot Program for Home Respiratory Rehabilitation at the Virgen Macarena University Hospital**

### **BACKGROUND AND CURRENT STATE OF THE SUBJECT**

Bronchiectasis not associated with cystic fibrosis (non CF bronchiectasis) is bronchial dilatations characterized by inadequate mucociliary clearance, whose main clinical expression is cough with purulent expectoration and dyspnea, leading to exercise limitation. In order to try to quantify the severity of the disease and its prognosis, in recent years different scales have been developed that take into account clinical, radiological and functional parameters (FACED and BSI).

The objective of the treatment of the disease lies in the prevention of exacerbations, reduction of symptoms, improvement in quality of life and stabilization of lung function (Polverino et al. 2017). Based on these objectives, we have tried to develop tools, until now not available in all media, such as the development of specific respiratory rehabilitation programs (PRR). Although the long-term benefits of PPRR have not been objectified or demonstrated, there is a common consensus on the need to include this type of intervention in the management of patients with bronchiectasis (strong level of recommendation) (Polverino et al. 2017), since they could stabilize lung function and exercise capacity, as well as influence exacerbations, although more studies are still needed in this regard. On the other hand, it is also not very clear where and when to carry out this type of program, and there is a need to implement and optimize respiratory rehabilitation programs in non-traditional settings, at home or in an exacerbation (Rochester et al. 2015) (Wedzicha et al. 2017)(Pasteur et al. 2010).

Most of the studies carried out in relation to RR and non-CF bronchiectasis have focused on outcomes on quality of life and lung function with disparate results (Annemarie L Lee et al. 2014), however there are fewer data in relation home base rehabilitation program . To date, there are several clinical trials that analyze exercise capacity and tolerance in patients with bronchiectasis undergoing RP, with a clear improvement in these parameters after completion (Murray, Pentland, and Hill 2009)(Zanini et al. 2015)(Singh et al. 2014)(J. Bradley, Moran, and Greenstone 2002).

The most recent meta-analysis (Annemarie L. Lee et al. 2017) includes four clinical trials with the aim of evaluating the effect of respiratory rehabilitation (RR) in terms of exercise capacity and tolerance, exacerbations, symptoms, quality of life and mortality.

## WORK HYPOTHESIS

Exercise tolerance and capacity can be modified after completing a respiratory rehabilitation program with a decrease in the perception of symptoms, exacerbations and quality of life.

## SPECIFIC OBJECTIVES

### Primary

To determine the capacity and tolerance to exercise by means of a cardiopulmonary test and to assess the effects and changes after a PRR in patients with BE without CF.

### Secondary

Assess the degree of baseline physical activity of patients with BE without CF and its changes after PR.

Know the severity through the prognostic scale E-FACED

Determine the impact of PR on health-related quality of life and anxious/depressive state, symptoms, exacerbations

## METHOD

- **Population (inclusion and exclusion criteria).**

The study population will be the patients of the monographic consultation of Bronchiectasis of the Virgen Macarena University Hospital.

### Inclusion criteria

- Established radiological diagnosis of bronchiectasis (HRCT of the chest).
- Non-CF bronchiectasis older than 18 years.
- Non-CF bronchiectasis in a stable situation, who have not required antibiotic therapy in the last 6 weeks.
- Dyspnea greater than 1 according to the modified scale of the Medical Research Council (mMRC).

### Exclusion criteria

- Smokers or former smokers of less than 6 months or with a history of consumption of 15 packs/year.
  - Cystic fibrosis.
  - Active infections (bronchopulmonary aspergillosis, pulmonary tuberculosis).
  - Active tuberculosis.
  - poorly controlled asthma

- Chronic obstructive pulmonary disease.
- Diseases that prevent adequate performance of exercise (neuromuscular pathology or residual injuries)
- Medical diseases that put the individual at risk of a decompensation due to the performance of any physical activity or cardiopulmonary stress test (unstable ischemic heart disease, acute myocardial infarction less than 1 month).
- Pregnancy.
- Mental disorder that prevents the adequate interpretation of the indications or performance of the tests.

- **Study design.**

Prospective and randomized study with consecutive inclusion of patients from the Non-CF bronchiectasis BE monographic clinic of the Virgen Macarena Hospital (Seville). Patients who meet the inclusion criteria will be randomized into two groups: control and intervention, patients will be assigned to each group using a numerical sequence generated by computer until the sample size is obtained.

The control group will receive basic recommendations on physical activity and the intervention group will be included in a mixed respiratory rehabilitation program (combining home and hospital sessions).

**Visit 1:** inclusion of patients with BE who comply with inclusion. Signature of informed consent and randomization of patients.

**Visit 2:** All patients will undergo an initial assessment of the degree of physical activity by means of accelerometers (®Sensewear arm band) for 3 days including weekends, as well as pulmonary function and exercise tolerance tests, stratification of severity according to the E-FACED scales.

\* Control group: written recommendations on performing some physical activity for at least 30 minutes of moderate intensity according to the recommendations of the Spanish Society of Pulmonology and the Andalusian Society of Pulmonology and Thoracic Surgery. (Casilda Olveira, Costa, and Martínez-García 2016) , (C Olveira et al. 2010). A phone call every 15 days to assess the physical activity carried out without talking about exercise or physical activity.

\* Intervention group: Patients will be included in an 8-week outpatient program with recall sessions led by our physiotherapist once every 2 weeks in the hospital's Respiratory Rehabilitation gym. In the first session, patients will be instructed on how to perform home exercises as well as how to use the Borg scale. A phone call weekly to provide support and general advice about exercise or physical activity.

The program will combine isotonic strength and resistance exercises. Resistance training will consist of bicycle or walking exercises (depending on the availability of each patient), with a progressive increase in distance or time of completion depending on symptom control.

The strength training program will include upper and lower limb exercises that will begin with no load and to which weights will be progressively added depending on the control of symptoms, in 2 sets of 6-8 repetitions:

- Hanger (to work the latissimus dorsi muscle).
- Butterfly (pectoralis major muscle work).
- Neck press (brachial triceps and deltoid work).
- Flexion of legs (work of biceps femoris and gastrocnemius).
- Extension of legs (work of quadriceps femoris): place a weight or ballast. Stretch the leg and raise the thigh
- Exercises with elastic bands: upper and lower limbs. Separate both ends of the tape as much as possible.
- Walking: increase the walking time progressively.
- Bicycle or treadmill: submaximal exercise. Constant pedaling at about 60 rpm with moderate intensity.

Patients will be encouraged to maintain the exercises after the study.

**Visits 3, 4 and 5:** at 8 weeks (time of completion of the rehabilitation programs), 6 months and 12 months, respectively. At the end-of-program and follow-up visits, all the measurements made at the baseline visit will be repeated, as well as the record of exacerbations.

All patients will receive an educational program about their disease as well as an individualized respiratory physiotherapy program including relaxation techniques, secretion management and assessment of nutritional status.

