### Measurement methods and variables

- **Assessment of exercise capacity with cycle ergometry.** Cycle-ergometry will be performed in progressive steps of one minute up to its maximum. We will use a state-of-the-art Vyntus CPX ergospirometer from the firm Jaeger-CareFusion. Maximum oxygen consumption, aerobic-anaerobic thresholds, respiratory compensation point, ventilatory limitation study, calorimetry, forced spirometry F/V, slow spirometry + MVV, maximum voluntary ventilation, cardiac output and physiological dead space will be assessed. The subsequent evaluation of the data will be carried out through the Sentry program platform
- **6-minute walk test (6MWT):** it is carried out in an absolutely flat corridor with a length equal to or greater than 30m, placing cones to mark the ends of the route. The distance traveled in a period of 6 minutes will be

calculated according to the recommendations of the American Thoracic Society (ATS)

- **Physical activity level** using the Multisensor ArmBand accelerometer. (SenseWear mini armband; BodyMedia,) as referenced in the study by [name] et al ([name] 2016). It is placed on the right triceps and provides information on calorie consumption and physical activity levels, which are subsequently, analyzed using specific software (INNERVIEW professional version 8, BodyMedia, Pittsburgh, PA). ↗ Quality of life in Saint George respiratory questionnaire (Soto Campos 2009). 50 items divided into three scales: symptoms, activity and impact. Symptom scale items refer to frequency and severity of respiratory symptoms
- **Cough Severity Questionnaire with LCQ** (Murray et al. 2009)(Annemarie L. Lee et al. 2017). The LCQ measures the physical, psychological, and social impact of chronic cough. It consists of 19 items. Validated in BQ not CF.
- **Severity and prognosis by E-FACED:** number of exacerbations in the previous year; F: percentage of predicted FEV1; A: age; C: chronic colonization by *Pseudomonas aeruginosa*; E: Extension [number of lung lobes affected by bronchiectasis]; D: dyspnea) have been proposed to stratify BE patients according to their main dimensions (symptoms, lung function, imaging, and microbiology). 0-3 points: mild bronchiectasis. 4-6 points: moderate bronchiectasis. 7-9 points: severe bronchiectasis
- **Pulmonary function test:** measurements through a Jaeger Viasys Mastercope spirometer. Forced expiratory volume in 1 s (FEV1), Forced vital capacity (FVC).

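### Patients are randomised at Visit 1, before the Visit 2 baseline is measured, and nothing in the supplied text withholds the allocation until that baseline is complete

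*Combined protocol and SAP*

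**What the plan says.** All references are to the combined protocol and SAP.

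- **Study design, Visit 1:** eligible patients are included, with "Signature of informed consent and randomization of patients".
- **Study design, Visit 2:** "All patients will undergo an initial assessment of the degree of physical activity by means of accelerometers", worn "for 3 days including weekends, as well as pulmonary function and exercise tolerance tests". E-FACED severity is also graded here. The content of each arm follows under the same visit. For controls it begins with "written recommendations on performing some physical activity for at least 30 minutes of moderate intensity"; for the intervention arm it is the 8-week programme.
- **Study design, Visits 3, 4 and 5** (8 weeks, 6 months and 12 months): "all the measurements made at the baseline visit will be repeated". The Visit 2 values are thus the reference for every later comparison.
- **Allocation:** the only text is that a computer-generated numerical sequence assigns patients. The supplied text does not mention concealment, masked assessors or the moment of disclosure.
- **Work calendar:** the programme starts once recruitment has ended and the initial tests are done.

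**The concern.** A baseline is safest when neither the patient nor the tester can know the arm while it is recorded. Here the order of visits gives no such assurance, and several of the values depend on effort or behaviour. The primary objective uses a cardiopulmonary test "to assess the effects and changes after a PRR in patients with BE without CF", and under Measurement methods and variables "Cycle-ergometry will be performed in progressive steps of one minute up to its maximum", so the result depends partly on how hard the patient is willing to work and is encouraged to work. The 6-minute walk has the same weakness. A secondary objective is to "Assess the degree of baseline physical activity of patients with BE without CF and its changes after PR", and three days of free-living activity is the measure most open to change by someone who knows their group. Lung function and some cycle-test variables may be less exposed.

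If the arm is known and shifts the baseline in one group, change from baseline is distorted, and baseline-adjusted comparisons usually less so. The distortion could imitate a benefit or hide one.

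Separately, any patient who leaves between the two visits would count as randomised but have no baseline, and hence no change score, in a trial of 30 per arm.

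**Working it through.** **1. Order of procedures.**

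| Step | Where stated | Timing |
|---|---|---|
| Consent and randomisation | Study design, Visit 1 | First |
| Accelerometry, lung function, exercise tests, E-FACED | Study design, Visit 2 | After randomisation |
| Disclosure of the arm | Not stated | Unknown |
| Control group's written advice | Listed under Visit 2 | Not placed relative to the end of the recording |
| Start of the programme | Work calendar | After the initial tests |

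The Work calendar makes the baseline precede the programme. It does not make it precede knowledge of the arm. This establishes the point without arithmetic.

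**2. Can its size be derived?** No. The Statistical analysis section gives 95% power, 15% loss and 30 per group, but no SD, effect size or correlation. Its between-group t test does not say whether it uses follow-up values or changes.

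**3. Illustration, before and after the fix.** *From the document:* 30 × 0.85 = 25.5, taken as n = 25 evaluable per arm; significance level 5%. *Assumed:* two-sided test, unit SD at both times, correlation ρ = 0.6 or 0.8, no true effect, and shifts b (baseline) and g (follow-up) in the same arm caused only by knowing the allocation. The noncentrality parameters are:

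- change score: (g − b)/√(2(1 − ρ)) × √(n/2), 48 df
- ANCOVA: (g − ρb)/√(1 − ρ²) × √(n/2), 47 df
- follow-up value only: g × √(n/2), 48 df

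Worked case, b = 0.2, g = 0, ρ = 0.6, change score: −0.2/√0.8 × √12.5 = −0.79, giving a type I error of 12.1%.

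The fix sets b = 0 and leaves g as it was. Type I error, ρ = 0.6 / 0.8:

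| Shift without the fix | Analysis | Before | After |
|---|---|---|---|
| b = 0.2, g = 0 | Change | 12.1% / 19.5% | 5.0% / 5.0% |
| | ANCOVA | 8.1% / 15.2% | 5.0% / 5.0% |
| | Follow-up only | 5.0% | 5.0% |
| b = 0.2, g = 0.1 | Change | 6.7% / 8.5% | 6.7% / 8.5% |
| | ANCOVA | 5.1% / 6.4% | 7.2% / 8.9% |
| | Follow-up only | 6.4% | 6.4% |
| b = 0.2, g = 0.2 | Change | 5.0% / 5.0% | 12.1% / 19.5% |
| | ANCOVA | 6.4% / 5.6% | 13.9% / 21.1% |
| | Follow-up only | 10.7% | 10.7% |

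The fix lowers the error only in the first block. In the second it leaves the change score where it was and raises ANCOVA. In the third it raises both, because an equal shift at the two times had been cancelling in the change score. That cancellation is accidental and is no reason to keep an unprotected baseline, but the table cannot be used to promise a lower error rate.

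**The case against.** The strongest reply is that randomising and disclosing are different acts. A reader might infer that patients learn their arm at Visit 1; the document does not say so. This is a short protocol, and part of the file was not available for review, so silence on disclosure is weaker evidence than usual. That stands, and it limits the claim to possible bias. It does not remove the point, because the order of randomisation and baseline is stated outright and no safeguard accompanies it in the supplied text.

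Other stronger readings also fail:

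- **Control advice contaminates the activity baseline.** The advice is listed under Visit 2, but so is the intervention programme, which the Work calendar starts only after the tests. The list describes what each arm receives and does not fix when. Advice given during the recording is possible, not stated.
- **Losses before baseline are expected.** Potential Job Limitations foresees losses during the study generally, and 15% is allowed for. Neither refers to the gap between Visits 1 and 2, whose length is not given.
- **The treatment effect will be inflated.** Nothing in the document fixes a direction.
- **Moving randomisation will reduce type I error.** No masking at follow-up is described, so a shift confined to baseline is arguably the least natural of the three cases, and it is the only one in which the fix helps on this measure.

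It is also fair to say that ANCOVA is not in the plan, and that a between-group test on follow-up values alone would be untouched by a baseline-only shift.

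**Conclusion.** The point holds in a limited form. Randomisation precedes the baseline on which every later comparison rests, and the supplied text does not keep the allocation from patients or assessors while that baseline is measured. Bias in the effort- and behaviour-dependent values is therefore possible. Its size and direction cannot be determined from the document. Any patient lost between the two visits would be randomised without a baseline, but the likely number is unknown.

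The type I error figures rest wholly on assumed shifts and correlations, and apply one shift to all outcomes for simplicity. They show that the effect could matter at this sample size and that it depends on what happens at follow-up; they do not estimate the effect. The design should be corrected because a baseline measured before allocation is known is sound in itself and cheap to secure here. Confidence is moderate, since disclosure may already be delayed in practice.

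**What to change.** Adopt one of two arrangements and write it into Study design:

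1. Take consent and issue the armband at Visit 1, complete every baseline measurement by Visit 2, including the full 3-day recording with its weekend days, and only then randomise.
2. Keep randomisation at Visit 1, but state that the allocation and all arm-specific material are withheld from patients and assessors until the last baseline measurement, including the accelerometer recording, is complete.

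The first also ensures that nobody is randomised without having completed the baseline; the second does not.

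**Cost.** No extra test or patient is needed, and the programme need not be delayed, since the Work calendar already starts it after the initial tests. Patients learn their arm slightly later. The first option needs an interval between visits long enough for the recording, and armbands available at Visit 1; the document states neither. The second may need one extra contact to hand over arm-specific material once the armband is back.

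**What it does not do.** It makes the baseline a measurement taken before the allocation is known. It does not deal with unmasked follow-up testing, and it does not turn the within-group paired test in the Statistical analysis section into a test of the treatment effect. If type I error figures accompany the change, show them before and after it and label them as illustration.

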## Statistical analysis

For the calculation of the sample size, a power of 95% is used, a hypothetical loss rate during the study of 15%, a total of 30 patients per group would be included, enough to demonstrate our hypothesis and find statistically significant differences in the capacity of exercise and the change in physical activity in the two populations.

Statistical analysis was performed using the statistical analysis software IBM SPSS Statistics (SPSS v23, Chicago, IL, USA). For quantitative variables, the values are expressed as mean +/- standard deviation, while in the case of qualitative variables; their values are included as frequency and percentage. The comparison between groups was carried out using the T test for independent samples in the event that the data behaved according to a normal distribution. Otherwise, the Mann-Whitney U test was used for independent samples. The comparison of the effects of respiratory rehabilitation was performed with the Student's t test for related samples when the data follow a normal distribution and the Wilcoxon signed rank test for related samples. In all cases, the minimum level of significance was considered to be  $p < 0.05$ . If statistically significant differences are identified between the different groups studied, "a posteriori" comparison tests will be carried out, such as the Mann-Whitney U test according to application criteria, with the level of significance corrected.

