## Potential Job Limitations

Due to the natural history of the disease, we cannot foresee decompensations, so there may be losses in the development of the study, having to increase the sample size from the outset.

In this study, since it is a home program, this may be greater due to the lack of stimulation generated by the groups to carry out physical activity.

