## Work calendar

Once the 3-month recruitment period has ended and the initial assessment tests have been completed, an 8-week rehabilitation program will begin with a subsequent 12-month follow-up from the start of the PRR. After this, the analysis, exploitation of the data and subsequent dissemination of the results will be carried out.

- **Data exploitation period:** once the recruitment period has ended, the collected data will be analyzed and exploited, with the aim of subsequently disseminating the results.

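### Exacerbations have no defined unit or window, and the only between-group test ignores time at risk, so unequal losses would distort a comparison of counts

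*Combined protocol and SAP*

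**What the plan says.** - **Objective.** The secondary objectives include "Determine the impact of PR on health-related quality of life and anxious/depressive state, symptoms, exacerbations". No definition of an exacerbation, unit of analysis or time window is given.
- **Collection.** Under METHOD, Visits 3, 4 and 5 take place "at 8 weeks (time of completion of the rehabilitation programs), 6 months and 12 months, respectively", and at these visits "all the measurements made at the baseline visit will be repeated, as well as the record of exacerbations". The Work calendar describes the programme "with a subsequent 12-month follow-up from the start of the PRR".
- **The only numeric form.** Measurement methods and variables lists "number of exacerbations in the previous year" as a component of E-FACED. This is a baseline severity item, not the outcome.
- **Analysis.** Statistical analysis has one general rule: "The comparison between groups was carried out using the T test for independent samples" when data are normal; "Otherwise, the Mann-Whitney U test was used for independent samples". It contains no rate or count model, no time-to-event method, no analysis set and no rule for patients lost before 12 months.
- **Losses.** Statistical analysis allows for 15% loss, not split by arm. Potential Job Limitations says "we cannot foresee decompensations, so there may be losses in the development of the study", and adds an ambiguously worded remark that this limitation may be larger in a home programme.

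**The concern.** A patient who leaves at 8 weeks can contribute events from 8 weeks only; one who completes contributes a year. Both tests would treat the two totals as like for like. If one arm loses more follow-up, its mean count falls and it looks better without any treatment effect. The reverse pattern hides a real effect.

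Equal retention cannot be presumed. The arms differ in contact: weekly calls and fortnightly gym sessions in one, a call every 15 days in the other. The plan itself ties losses to decompensations, which are close to the outcome. What is at stake is the trial's statement about exacerbations, which also supports the cost argument in the section on practical applicability.

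**Working it through.** **Inputs from the documents:** 30 patients per group, 15% overall loss, follow-up to 12 months with visits at 8 weeks and 6 months, significance level 0.05 (taken as two-sided).

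**Assumed, because the documents give no figure:** control rate 1.5-2.5 events a year (1-3 in a second set of runs), gamma-Poisson counts with dispersion 0.5, and the split of losses between arms. Losses are unrelated to a patient's event rate except in step 5.

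**The plan's own figure.** The 30 per group cannot be reproduced, because no effect size or SD is stated. It also concerns exercise capacity and physical activity, not exacerbations, so it does not bear on this point.

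**1. Mean time at risk and the ratio it produces.** Let p be the fraction lost in an arm. With losses uniform over the year, mean follow-up is 1 − p/2 years. With all losses at week 8 it is 1 − p(1 − 8/52) = 1 − 0.846p. With no true effect, the expected ratio of raw mean counts equals the ratio of mean follow-up. A 5% / 25% split averages the planned 15%.

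| Loss, control / intervention | Timing | Follow-up, control | Follow-up, intervention | Raw ratio, no effect |
|---|---|---|---|---|
| 15% / 15% | uniform | 0.925 | 0.925 | 1.00 |
| 5% / 25% | uniform | 0.975 | 0.875 | 0.875/0.975 = 0.90 |
| 5% / 25% | week 8 | 0.958 | 0.788 | 0.788/0.958 = 0.82 |
| 25% / 5% | uniform | 0.875 | 0.975 | 0.975/0.875 = 1.11 |

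Simulated raw ratios agree: 0.89-0.91 for the 5% / 25% uniform case and 0.82-0.84 for week 8.

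**2. Type I error, no effect, 5% / 25% split (simulation).**

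| Timing | t test and Mann-Whitney | Negative binomial, offset, dispersion estimated |
|---|---|---|
| uniform | about 6-8% | about 5-6.5%, ratio about 1.0 |
| week 8 | about 7-12% | about 5-6.5%, ratio about 1.0 |

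A separate set of runs over rates of 1-3 a year, 3,000 trials per scenario, put the week-8 figures at 9-11% (t test) and 10-16% (Mann-Whitney), so the upper end depends on the assumed rate. A person-time rate comparison stayed at about 5-6% there.

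**3. Equal 15% losses.** Both planned tests keep about 5% error. For a true halving of the rate, power is 45-57% (Mann-Whitney), 51-65% (t test) and 57-71% (negative binomial). Part of the model's lead reflects a type I error slightly above 5%.

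**4. A real effect hidden.** Take a true ratio of 0.6, a control rate of 2 a year, and losses of 25% control / 5% intervention. The expected raw ratio is 0.6 × 0.975/0.875 = 0.67 (uniform) or 0.6 × 0.958/0.788 = 0.73 (week 8; 0.72 simulated). Compared with equal losses, Mann-Whitney power falls from 33% to 19% (uniform) or from 30% to 11% (week 8). The person-time analysis holds at about 42-43%.

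**5. Losses that follow an exacerbation.** With no true effect and about 6% control / 24-26% intervention lost after an event, the completers-only ratio is 0.75-0.80 (Mann-Whitney error about 12%), the raw-count ratio 0.84-0.85, and the person-time ratio about 0.95. Person-time reduces the bias but does not remove it. Dropping incomplete patients makes it worse.

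**The case against.** **The plan does not say that raw counts will be compared.** A reader might infer that it does. The documents support only a default reading: an exacerbation record is most naturally a number, and the general rule for quantitative variables would then apply. Exacerbations could instead be analysed as annualised rates under the same tests, or as any versus none, for which the plan names no test. This objection stands, and it makes the missing definition part of the point. Under the any-versus-none reading, unequal follow-up would still matter.

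**Unequal loss is an assumption.** A reader might infer that the home arm will lose more. The remark in Potential Job Limitations is ambiguous and gives no figure, and the 15% is not split by arm. With equal losses the planned tests are valid under the null. With losses unrelated to event rates, a completers-only comparison also kept about 5% error. This stands too: the bias is conditional.

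**The count model is not a clear winner on type I error.** With losses spread over the year, 5-6.5% against 6-8% is a small difference. The firmer gains are the unbiased ratio, protection when losses come early, and some power.

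**An offset does not cure informative loss.** True; step 5 of the working shows about 5% residual bias. Hence the sensitivity analysis in the fix.

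**Conclusion.** The point holds conditionally. The plan neither defines the exacerbation outcome nor provides a between-group method that accounts for time at risk. If counts are compared and follow-up differs between arms, the comparison is biased in whichever direction the losses run: modestly if losses are spread over the year, and more if they come early. The sizes rest on assumed event rates, dispersion and loss splits, none of which the documents give. With equal losses the cost is limited to some power.

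Two stronger readings are not supported. The documents do not show that the exacerbation result will be wrong, since that needs unequal follow-up and truncated counts kept in the analysis, or losses related to the outcome. Nor does the point reach the primary objective: exercise capacity and the 30 per group are unaffected. It is a change that should be made to a secondary analysis.

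**What to change.** In Statistical analysis, state that:

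- the outcome is the number of exacerbations from baseline to 12 months or last contact, whichever is earlier, with an exacerbation defined and the same starting point used in both arms (the Work calendar counts from the start of the programme, which control patients do not have);
- arms are compared as randomised with a negative binomial model, dispersion estimated, log(follow-up time) as offset, and the previous-year count already collected for E-FACED as covariate;
- the rate ratio is reported with its 95% CI, and patients lost early are included up to last contact;
- a sensitivity analysis addresses losses related to exacerbations, because the offset reduces that bias without removing it.

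The cost is a few lines of text and one date per patient. The model is available in SPSS under generalized linear models. The downside is that last-contact dates must be recorded, and they may be hard to reconstruct later, so this should be settled before the data are analysed.

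### The follow-up exacerbation window is not stated and no time-at-risk adjustment is planned, so a before-after test against the previous-year count would not be valid at 8 weeks or 6 months

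*Combined protocol and SAP*

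**What the plan says.** Exacerbations are a stated outcome. The secondary objectives include: "Determine the impact of PR on health-related quality of life and anxious/depressive state, symptoms, exacerbations".

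The only exacerbation window given anywhere is in the E-FACED description (Measurement methods and variables): "number of exacerbations in the previous year". E-FACED is collected at Visit 2, listed under Study design as "stratification of severity according to the E-FACED scales".

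Visits 3, 4 and 5 take place "at 8 weeks (time of completion of the rehabilitation programs), 6 months and 12 months, respectively". At these visits "all the measurements made at the baseline visit will be repeated, as well as the record of exacerbations". The period covered by that record is not stated.

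The Statistical analysis section gives an independent-samples t or Mann-Whitney test between groups. For change it says: "The comparison of the effects of respiratory rehabilitation was performed with the Student's t test for related samples", with a Wilcoxon signed rank test as the alternative. No test is assigned to a named outcome, and there is no rate, offset or equal-window rule for counts.

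**The concern.** A count depends on how long one counts. The baseline figure spans a year, while the first two follow-up visits come only 8 weeks and 6 months after the start. The paired procedure is the one the plan describes as measuring the effects of rehabilitation, and it exempts no outcome. If it is run on raw exacerbation counts, a shorter follow-up window can look like clinical improvement. This would happen with complete follow-up and in both arms, so it is separate from dropout.

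At stake is whether a within-arm fall in exacerbations could be reported as a benefit when the underlying rate has not moved. The section on practical applicability hopes for fewer admissions and emergency visits through better exacerbation control, and an artefact of this kind would appear to support that hope.

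**Working it through.** **Inputs from the documents.** Baseline window: 52 weeks (E-FACED). Visits: 8 weeks, 6 months (about 26 weeks) and 12 months (about 52 weeks). Patients: 30 per group with 15% loss, and 30 × 0.85 = 25.5, so about 25 to 30 analysed per arm. Entry requires no antibiotic therapy in the previous 6 weeks. The plan states no exacerbation rate or expected reduction, so it has no figure of its own to reproduce here.

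**Step 1: apparent fall at a constant rate.** The formula is 1 − (follow-up window ÷ 52). Three readings of the follow-up record fit the text.

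| Reading of the record | 8 weeks | 6 months | 12 months |
|---|---|---|---|
| Since last visit | 1 − 8/52 = 84.6% | 1 − 18/52 = 65.4% | 1 − 26/52 = 50.0% |
| Since baseline | 1 − 8/52 = 84.6% | 1 − 26/52 = 50.0% | 1 − 52/52 = 0% |
| Previous 12 months | 0% | 0% | 0% |

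The 18 weeks are 26 − 8.

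**Step 2: what the third reading measures.** A previous-year count taken at 8 weeks contains 52 − 8 = 44 weeks from before baseline. At 6 months it contains 52 − 26 = 26 such weeks. Those weeks also belong to the baseline count, so the comparison cannot isolate change after the programme began. At 12 months the overlap is nil.

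**Step 3: sensitivity to the stability criterion.** Suppose the 6 antibiotic-free weeks carry no exacerbations. Baseline time at risk is then 52 − 6 = 46 weeks. Since-last-visit counts give 1 − 8/46 = 82.6%, 1 − 18/46 = 60.9% and 1 − 26/46 = 43.5%. A full 12-month count after baseline gives 1 − 52/46 = −13.0%, an apparent rise. This assumes that every exacerbation involves antibiotics, which the documents do not say.

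**Step 4: false-positive rate of the paired test, since-last-visit reading.** Counts were simulated with no change in rate: gamma-Poisson, gamma shape 2, 2,000 runs per setting, paired t and Wilcoxon tests at 0.05. Mean rates of 1, 2 and 3 exacerbations per year and the dispersion are assumptions; 25 and 30 patients follow from the plan.

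| Follow-up window | Range of rejection rates |
|---|---|
| 8 weeks | 97–100% |
| 18 weeks | 76–100% |
| 26 weeks | 47–95% |
| 52 weeks (equal to baseline) | 4.7–5.8% |

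**Step 5: between-arm comparison.** With 25 per arm, 2 exacerbations per year and no treatment effect, the Mann-Whitney test at a common visit rejected in about 4.0–5.2% of runs for windows of 8, 18, 26 and 52 weeks. Both arms share the window, so its length cancels.

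**The case against.** A reader might infer that the plan records exacerbations over 8, 18 and 26 weeks, and so is bound to show a fall of 50–85% and to report a false effect of treatment. The documents do not support that, for three reasons.

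- **The windows are inferred.** No section says that the record runs from the previous visit. If it runs from baseline, the 12-month comparison is 52 weeks against 52. E-FACED is among the repeated measurements, so its previous-year item would be repeated like for like. Against this, the exacerbation record is listed as additional to the repeated measurements, which points to a since-visit or since-baseline record. The text does not settle it.
- **The paired test is not tied to exacerbations.** The statistical section is generic and also provides a between-group test. No section names the E-FACED item as the baseline for the exacerbation outcome.
- **The trial is randomised.** Any fall created by the window would appear in the control arm too, and the between-arm test is not biased by it.

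These points stand. They make the concern conditional and rule out 50% as a firm lower bound. The applicability section also states hopes formed before any data, and does not rest on a paired result. None of this supplies a valid before-after exacerbation test at the two early visits: two readings produce a fall, and the third counts pre-baseline time again.

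**Conclusion.** The point holds as a conditional one about a secondary outcome. The plan leaves the follow-up window open and makes no allowance for time at risk. If the paired test is applied to exacerbations, its result at 8 weeks or 6 months is not valid under any of the three readings. At 12 months the windows match under the since-baseline and previous-year readings, apart from the stability-criterion effect, but not under the since-last-visit reading.

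The window shares are simple arithmetic from the visit schedule, given a reading and a constant rate. The false-positive rates also rest on the assumed exacerbation rates and dispersion, and apply only to the since-last-visit reading. The change is worth making: the error is large where it occurs, and correcting it costs almost nothing.

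**What to change.** In the description of Visits 3, 4 and 5, state that exacerbations are recorded from baseline onward, and give the definition used to count one.

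In the Statistical analysis section:

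- Make the effect on exacerbations the randomised between-arm comparison of the 12-month rate, for example by negative binomial regression with a person-time offset. Use the previous-year count already collected for E-FACED as a covariate.
- Do not test exacerbations before-after at 8 weeks or 6 months.
- Limit any within-arm description to the 12 months after baseline against the 12 months before, as rates per patient-year and without a treatment-effect claim. Note that the antibiotic-free entry criterion may lower the baseline count.

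This takes a few sentences and no new visit. What is lost is the early within-arm exacerbation results, which would not be valid. The sample-size statement refers to exercise capacity and physical activity, not exacerbations, so the between-arm estimate should be reported with its confidence interval and may be imprecise.
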